Cognitive Data Analysis: We will compare continuous cognitive index change scores (Newman MF et al, 2001) between patients who receive CN-105 vs placebo using a 2-sided t-test. Based on the cognitive change variance seen in MADCO-PC patients (SD=0.21), this study (with ≥ 117 CN-105 treated and ≥ 39 placebo treated patients) will provide 80% power with $\alpha=0.05$ to detect a half SD difference (i.e. 0.1 units) in CCI score between CN-105 vs placebo treated patients. Post-hoc ANOVA will determine if there are differences in cognitive index values by CN-105 dose level. We will also perform a chi-squared analysis (or Fisher’s exact test if needed) to determine whether the rate of POCD as a dichotomous outcome (defined by a 1 SD drop in any of the 4 cognitive domains we have previously studied- 1- verbal memory, 2- visual memory, 3- attention/concentration, and 4- executive function) differs between CN-105 vs placebo treated patients.

Delirium analysis: Patients will be divided into those with delirium (i.e., 1 or more positive delirium

assessments) vs those without delirium (no positive delirium assessments). We will compare delirium rates between CN-105 treated and placebo treated patients using a two-sided chi-square test. With an expected delirium rate of 40% in placebo treated patients, this study (with >117 CN-105 treated patients, and >39 placebo treated patients) will provide 80% power to detect a 25% lower absolute rate of delirium in CN-105 vs placebo treated patients. Post-hoc ANOVA testing will evaluate for differences in delirium rates between CN-105 drug dose level groups, with post-hoc pairwise comparison tests as appropriate. Additional post-hoc analyses will evaluate delirium duration and severity between CN-105 vs placebo treated patients.

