10.2 Sample Size

We planned to enroll up to 250 patients total in this phase 2 escalating dose study, to obtain three successive groups of 67 randomized patients each. *Because enrollment happens at consent, and not all patients that consent will be randomized, we will keep enrolling patients until we reach 67 consented and randomized patients in each cohort.* In each group of 67 patients, 50 will receive a given dose of CN-105 and 17 will receive placebo. In our recent MADCO-PC study, ~80% of patients returned for the 6 week assessment. Thus, enrolling 67 patients in each group ensures ≥ 52 patients (i.e. 39 CN-105-treated; 13 placebo-treated) will complete the 3 month postop assessment. Due to a clerical error by the Investigational Drug Services that prepares our drug/placebo doses, 69 patients were randomized to the first patient cohort rather than 67. There will be no baseline preoperative cognitive status inclusion/exclusion criteria. Our prior work suggests ~15% of Duke orthopedic surgery patients over age 60 have MCI, ~5% have dementia, and ~80% are cognitively normal. All primary analyses here will be performed on patients grouped together (independent of baseline cognitive status); exploratory analyses will examine effects stratified by baseline cognitive strata, dose level, and by APOE4 carrier status.

Given the aforementioned expected 5% AE rates in placebo-treated patients, at completion we will have >80% power (with $\alpha=0.05$) in a two-sample two-sided unpooled variance chi-square test to detect an absolute difference of 14.8% between grade II or higher AE rates seen in placebo vs CN-105 treated patients (pooling the three dose levels of CN-105 together). We will also track the rates of other grade II or higher AEs recorded by the patient's surgical team in the medical record; at study completion we will use 2-sided t tests to compare the rates of any other grade II or higher AEs between placebo vs CN-105 treated patients.

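### The 80% power stated for the cognitive endpoint does not follow from its inputs: 117 vs 39 patients give about 77% for half an SD, and 80% is reached at about 0.11 units (0.52 SD)

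*Combined protocol and SAP*

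**What the plan says.** The Cognitive Data Analysis paragraph of section 10.1.3 compares CCI change "between patients who receive CN-105 vs placebo using a 2-sided t-test". It takes its variability from an earlier study at the same centre: "Based on the cognitive change variance seen in MADCO-PC patients (SD=0.21". It then says that "this study (with ≥ 117 CN-105 treated and ≥ 39 placebo treated patients" "will provide 80% power", at alpha 0.05, "to detect a half SD difference (i.e. 0.1 units) in CCI score between CN-105 vs placebo treated patients".

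The 117 and 39 are three times the 39 CN-105 and 13 placebo completers per cohort in section 10.2. That section starts from 50 and 17 randomized per cohort and reports, for the same earlier study, that about "80% of patients returned for the 6 week assessment". It also records that "69 patients were randomized to the first patient cohort rather than 67", which brings the planned total to 203.

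**The concern.** With the test, alpha, SD, group sizes and effect size all printed, the reader can recompute the power directly. It comes out below 80% under either reading of the effect size. The two readings also differ: half of 0.21 is 0.105, whereas 0.1 units is 0.1/0.21 = 0.476 SD.

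Preventing postoperative cognitive dysfunction is one of the trial's stated aims, and CCI change is its continuous measure of cognition. If the comparison is null, readers will use the stated power to judge whether a half-SD effect could have been missed. On the printed inputs that risk is about 23%, not 20%.

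**Working it through.** **Inputs** (section 10.1.3): two-sided two-sample t-test, alpha 0.05, SD 0.21, n1 = 117 (three doses pooled), n2 = 39, difference of half an SD.

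**Formula.** Noncentrality = difference / (SD × √(1/n1 + 1/n2)), with n1 + n2 − 2 degrees of freedom. Power is the probability that a noncentral t variable exceeds the two-sided 5% critical value; the opposite tail is negligible.

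**Attempt to reproduce the plan's 80%.**

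- √(1/117 + 1/39) = 0.1849; degrees of freedom = 154; critical value = 1.975.
- Half an SD (0.105): noncentrality = 0.5/0.1849 = 2.704; power = **76.6%**.
- Literal 0.1 units: noncentrality = 0.476/0.1849 = 2.575; power = **72.6%**.
- 80% is reached at 0.521 SD × 0.21 = **0.109 units**. At 0.11 units, power is 80.4%.

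**Does the formula explain the gap?** No. The normal approximation gives 77.2% at 0.105 and 73.1% at 0.1. In 200,000 simulated t-tests, power was 76.5% at 0.105, 72.6% at 0.1 and 80.4% at 0.11. A simulation of the unequal-variance t-test (50,000 runs) gives 75.9% at 0.105.

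**Do larger groups explain it?** The sizes are printed as minimums, so the plan's return rate of about 80% can be applied to the numbers randomized:

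| Basis | CN-105 / placebo | Power at 0.105 | Power at 0.1 |
|---|---|---|---|
| Printed minimums | 117 / 39 | 76.6% | 72.6% |
| 80% of 150 / 51 (201 randomized) | 120 / 41 | 78.4% | 74.4% |
| 80% of 203, the two extra patients split 3:1 (assumed) | 122 / 41 | 78.6% | 74.6% |
| Both extra patients on placebo (assumed; most favourable) | 120 / 42 | 79.2% | 75.2% |

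The plan does not state how the two extra patients were allocated. No row reaches 80%. At 3:1 allocation, the smallest groups that give 80% for half an SD are 129 and 43, and for a literal 0.1 units 141 and 47.

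**Settings that give more than 80%, but are not those printed.** A one-sided test gives 85.3% at 0.105 and 82.1% at 0.1, but the plan specifies two sides. All randomized patients (150 / 51) give 86.6% and 83.2%, but section 10.2 allows for loss before the follow-up assessment.

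**The case against.** The strongest reply is that the sentence is right at its printed precision. If 80% is held fixed, the detectable difference is 0.52 SD or 0.109 units, which to one decimal is 0.5 SD and 0.1 units. This is a plausible account of how the figure arose, and it is a good reason to treat 0.1 as rounding and not as a second claim. It does not make the stated power correct: rounding a detectable difference down overstates the power to detect it.

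Second, the group sizes are floors and the return rate is approximate. Six-week cognitive testing may also be done by remote video, so completion of testing could exceed the earlier study's return rate. Power for half an SD reaches 80% at about 84% retention of 150 / 51 (80.3%; at 83% it is 79.8%). That is possible, but the plan does not assume it, and a power attached to minimum group sizes should hold at those minimums.

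Third, the SD is a two-digit figure; 0.205 would also print as 0.21 and gives 78.6% at 0.105 units. But 0.105 is then more than half an SD. At exactly half an SD, power depends only on the group sizes, so rounding of the SD cannot close the gap.

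It stands that little depends on this figure: section 10.2 does not derive the sample size from it.

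**Conclusion.** The stated 80% is not supported at the printed inputs. For half an SD, power is about 77% with 117 and 39 patients, a shortfall of about 3 points, and about 78.5% at 80% retention of 201 or 203 randomized patients, a shortfall of about 1.5 points. The difference detectable with 80% power at 117 / 39 is 0.109 units (0.52 SD), against 0.105 units for half an SD. The figures of 73% to 75% apply only if 0.1 units is meant literally, which is the less likely reading.

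The calculation assumes approximately normal change scores with a common SD of 0.21. This is a minor arithmetic error in a secondary endpoint's power statement.

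**What to change.** In the Cognitive Data Analysis paragraph of section 10.1.3, keep the inputs and restate the result in one of two ways:

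- 80% power to detect about 0.11 units (0.52 SD); or
- about 77% power to detect half an SD (0.105 units).

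Either way, the SD and unit expressions should agree. The cost is one sentence and a slightly less favourable figure. Sample size, visits, data collection and the analysis method stay as they are.

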10.2 Sample Size

We planned to enroll up to 250 patients total in this phase 2 escalating dose study, to obtain three successive groups of 67 randomized patients each. *Because enrollment happens at consent, and not all patients that consent will be randomized, we will keep enrolling patients until we reach 67 consented and randomized patients in each cohort.* In each group of 67 patients, 50 will receive a given dose of CN-105 and 17 will receive placebo. In our recent MADCO-PC study, ~80% of patients returned for the 6 week assessment. Thus, enrolling 67 patients in each group ensures ≥ 52 patients (i.e. 39 CN-105-treated; 13 placebo-treated) will complete the 3 month postop assessment. Due to a clerical error by the Investigational Drug Services that prepares our drug/placebo doses, 69 patients were randomized to the first patient cohort rather than 67. There will be no baseline preoperative cognitive status inclusion/exclusion criteria. Our prior work suggests ~15% of Duke orthopedic surgery patients over age 60 have MCI, ~5% have dementia, and ~80% are cognitively normal. All primary analyses here will be performed on patients grouped together (independent of baseline cognitive status); exploratory analyses will examine effects stratified by baseline cognitive strata, dose level, and by APOE4 carrier status.

Given the aforementioned expected 5% AE rates in placebo-treated patients, at completion we will have >80% power (with $\alpha=0.05$) in a two-sample two-sided unpooled variance chi-square test to detect an absolute difference of 14.8% between grade II or higher AE rates seen in placebo vs CN-105 treated patients (pooling the three dose levels of CN-105 together). We will also track the rates of other grade II or higher AEs recorded by the patient's surgical team in the medical record; at study completion we will use 2-sided t tests to compare the rates of any other grade II or higher AEs between placebo vs CN-105 treated patients.

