5.4.2 Handling of Participant Withdrawals or Terminations

A recent phase I trial did not identify any specific adverse events or safety concerns with CN-105 (Guptill J et al, 2017). Nonetheless, if at any time during the dosing period, participant safety is considered at risk due to study agent-related adverse events per the judgement of the external Data Safety Monitoring Board (or DSMB+) and the PI, then the study agent will be immediately discontinued. Although the DSMB+ is only scheduled to convene and review reports (including grade II or higher AE, and SAE information) at the completion of each 67 patient cohort, the PI may also request that the independent statistician prepare additional interim analyses and provide these to the DSMB+ at any time. For example, this may be useful and/or appropriate if there is a severe SAE (such as a patient death) and the PI wishes to have the DSMB+ review grade II or higher AE rates and data up to an including this severe SAE, and make interim recommendations to the study team.

Since CN-105 modulates the inflammatory response, it could theoretically impair the response to infection. Thus, in an abundance of caution, the study agent will be discontinued in any patient who develops any intracerebral or systemic infection.

If a participant has clinically significant laboratory and/or electrocardiographic abnormalities that are considered to be related to the study agent in the judgement of the Principal Investigator or the DSMB, study agent treatment discontinuation will be evaluated.

Primary study analyses will be conducted using intention to treat analysis (i.e. with patients included in the groups to which they were randomized even if they did not correctly receive all doses to which they were randomized); secondary analysis may be conducted using as treated analyses (i.e. with patients grouped by the drug doses actually received).

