7.4.2 Day 0 (Day of Surgery)

The following procedures and assessments will be conducted at this visit:

Collect CSF sample/ LP prior to surgery (if not done at the time of the Initial Consent and Visit)

Concomitant medications administered per standard of care.

Collect blood sample (if not done at the time of the Initial Consent and Visit)

Laboratory assessments

Study drug or placebo administration (within one hour prior to scheduled or actual surgery start time, and subsequent drug doses will be given every 6 hours thereafter until 3 days after surgery or hospital discharge, whichever comes first, up to a maximum of 13 doses) by the patient's clinical care team. Each case start time will be defined by the study team as either the start of the surgery/procedure or the start of anesthesia. If the case gets delayed by more than 6 hr and we've already given the first dose, we will give an additional dose prior to surgery, but under no conditions will the patient be given more than 13 doses total of CN-105.

EEG (within 2 hours before surgery as well as during and just aftersurgery). In the event that sufficient personnel or equipment are unavailable, or in the event that two MARBLE patients are having surgery at the same time, or in the event that there is insufficient time to place the EEG sensor on that patient's head before the start of surgery, the study team may not record EEG from all patients or at all points before, during, and just after surgery/anesthesia. Auditory tones will be played and auditory event-related potentials will be recorded if the pre-op and surgical workflow allows and if study personnel are available.

Vital signs (including heart rate) will be obtained and entered into the anesthetic record during the surgery by the clinical care team as per GCP, standard of care, and the American Society of Anesthesiology guidelines .

Continuous heart rate monitoring will be obtained for up to 15 minutes prior to surgery and during the surgery, to assess heart rate variability (R-R interval) as an index of vagal nerve function.

Grade II or higher AEs (and all SAEs) will be monitored and recorded from just after the first study drug or placebo administration until the end of the 6 week +/- 3 weeks postoperative study follow up visit.

Delirium Screening may be administered with 3D-CAM or CAM-ICU up to two times after surgery.

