10.1.2 Safety and Feasibility Endpoints

Safety Analysis: Our DSMB will examine all grade II or higher AEs and all SAEs in CN-105 and placebo treated patients. The expected rate of moderate and severe adverse events in this patient population is 5% each, based on historical Duke orthopedic surgery data; thus we expect similar AE rates in this trial in placebo- treated patients. At the end of each 67 patient randomized group, the DSMB will examine grade II or higher AE rates in drug-treated vs placebo-treated patients, and consider whether the study should be stopped or whether other corrective action should take place. An independent statistician will prepare summary reports (including all grade II or higher AE rates in drug vs placebo treated patients) for review by the DSMB+ at the end of each 67 patient randomized group. Thus, the study team (and the primary study statistician) will thus remain blinded to patient treatment assignment throughout the course of the study. Due to a clerical error by the Investigational Drug Services that prepares our drug/placebo doses, 69 patients were randomized to the first patient cohort rather than 67. Additionally, because enrollment happens at consent, and not all patients that consent will be randomized, we will keep enrolling patients until we reach 67 consented and randomized patients in each of the last two cohorts.

Assuming that we continue with all three dose groups, at study completion we will have ≥ 117 total CN-105 treated patients and ≥ 39 placebo-treated patients. Given the aforementioned expected grade II or higher AE rates in placebo-treated patients, at completion we will have $>80\%$ power (with $\alpha=0.05$) in a two- sample two-sided unpooled variance chi-square test to detect an absolute difference of 14.8% between grade II or higher AE rates seen in placebo vs CN-105 treated patients. We will also track the rates of other grade II or higher AEs recorded by the patient’s surgical team in the medical record; at study completion we will use 2 sided t tests to compare the rates of any other grade II or higher AEs between placebo vs CN-105 treated patients.

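### The only test named for the primary adverse-event comparison does not hold its 5% level: at the plan's 5% event rate its exact type I error is 9.1% (150 vs 51) or 12.5% (117 vs 39)

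*Combined protocol and SAP*

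**What the plan says.** Section 10.2 (Sample Size) takes a 5% placebo rate, pools the three dose levels, and states that "at completion we will have >80% power" at alpha 0.05 in a "two-sample two-sided unpooled variance chi-square test to detect an absolute difference of 14.8" percentage points. Section 10.1.2 repeats the test ("unpooled variance chi-square test to detect an absolute difference of 14.8" points) and gives the counts behind it: at least 117 CN-105 and at least 39 placebo patients. The rate comes from the same section: "The expected rate of moderate and severe adverse events in this patient population is 5% each".

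No other test, continuity correction or small-count fallback is given for this comparison. The t tests in 10.1.2 and 10.2 are for any other grade II or higher events. Fisher's test appears as a fallback once, in 10.1.3, and only for dichotomous cognitive decline: "exact test if needed) to determine whether the rate of POCD as a dichotomous outcome".

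On the analysis set, section 5.4.2 says: "Primary study analyses will be conducted using intention to treat analysis (i.e. with patients included in the groups to which they were randomized". Three cohorts of 50 and 17 give 150 vs 51 randomized. The 117 and 39 are the 6-week completers (39 and 13 per cohort, from about 80% return).

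**The concern.** The unpooled statistic divides the difference in rates by a standard error built from each arm's own observed rate. With a small arm and a rare event, that arm will sometimes have no events. Its estimated variance is then zero, the standard error is too small, and a handful of events in the large arm is declared significant. A 3:1 allocation with a 5% rate is the setting in which this happens.

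The primary safety result is at stake. A test run at a nominal 5% could report a harmless drug as significantly more harmful far more often than 2.5% of the time, and the power quoted alongside it would be flattered by the same excess.

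**Working it through.** **Inputs.** Two-sided alpha 0.05, unpooled variance, 5% placebo rate, 14.8-point difference (10.2); 117 and 39 (10.1.2); 150 and 51 (3 × 50 and 3 × 17, section 10.2).

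**Method.** With x1 events in n1 treated patients and x0 in n0 placebo patients, the named test rejects when |x1/n1 − x0/n0| / sqrt[p1(1−p1)/n1 + p0(1−p0)/n0] > 1.96, where p1 and p0 are the observed rates. Summing Bin(n1, π1) × Bin(n0, π0) over all rejecting outcomes gives exact power (π1 ≠ π0) or exact size (π1 = π0).

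**The plan's own figure.** At 117 vs 39, with 5% vs 19.8%, exact power is 80.1%, and 80% power is reached at 14.78 points. The stated 14.8 is reproduced.

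**Exact size of the same test** (harm direction in brackets):

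| Common rate | 150 vs 51 | 117 vs 39 |
|---|---|---|
| 5% | 9.1% (8.4%) | 12.5% (11.8%) |
| 10% | 6.9% (5.7%) | 7.3% (6.0%) |
| 20% | 5.7% (3.9%) | 6.1% (4.3%) |
| Minimum over 2% to 50% | 5.4% | 5.9% |

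Cohort 1 took 69 patients instead of 67, so the randomized total becomes 203. The plan does not give the split. Assuming 152 vs 51 or 151 vs 52, the size at 5% is 9.2% or 8.9%.

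**Where the excess comes from.** The chance of no placebo events is 0.95^51 = 7.3% or 0.95^39 = 13.5%. The test then rejects from four treated events upward. At 5% that has probability 94.5% with 150 patients and 84.2% with 117. The products are 0.0731 × 0.945 = 6.9 of the 9.1 points, and 0.1353 × 0.842 = 11.4 of the 12.5 points.

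**Example.** Take 4/150 vs 0/51. The difference is 0.0267 and the standard error is sqrt(0.0267 × 0.9733/150) = 0.01315, so z = 2.03 and p = 0.043. Fisher's test gives p = 0.57, and the score 95% interval for the difference runs from −4.4 to +6.7 points.

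**Other tests.** Size at a 5% common rate, power at 5% vs 19.8%:

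| Test | Size, 150/51 | Power, 150/51 | Size, 117/39 | Power, 117/39 |
|---|---|---|---|---|
| Unpooled (named) | 9.1% | 87.8% | 12.5% | 80.1% |
| Pooled chi-square | 4.7% | 78% | 4.0% | 63% |
| Fisher | 3.2% | 74% | 2.7% | 62% |
| Doubled one-sided mid-p Fisher | 3.8% | 80.0% | 2.2% | 68% |

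For 80% power at a 5% placebo rate, the mid-p version needs 14.8 to 14.9 points at 150 vs 51 and about 17.5 at 117 vs 39. Fisher needs about 16 at 150 vs 51.

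**The case against.** - **The test is named only inside power statements.** This is true: no sentence commits the primary analysis to it, whereas the plan does commit to a method for other endpoints. But then the primary endpoint has no other named test, and the power claim at alpha 0.05 still rests on one that does not deliver alpha 0.05.
- **117 vs 39 is the wrong set, and a lower bound.** On the intention-to-treat set the relevant size is 9.1%, not 12.5%. The power dependence also largely disappears at 150 vs 51, where mid-p gives 80.0% and pooled chi-square 78%. Both points stand. The 12.5% figure matters because the stated power was calculated at those counts.
- **The true rate may be higher.** If the 5% each for moderate and severe events is summed, the rate is about 10% and the size 6.9% to 7.3%. At 20% the excess is small. This stands, but 10.2 uses 5%, and the size stays above 5% at every common rate from 2% to 50%.
- **Section 4.2.1 words the endpoint by dose cohort.** For 50 vs all 51 placebo patients the size at 5% is only 5.4%; for 50 vs 17 concurrent placebo it is 10.3%. The powered comparison is pooled (10.2), and 4.1 makes primary analyses independent of dose level.
- **The consequences are limited.** Stopping rests on event rates and the monitoring board's judgement (5.4.3, 8.6), and the error runs toward false harm, not false reassurance. This is fair, but the final primary safety conclusion is still affected.

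**Conclusion.** The concern holds. At the plan's 5% rate, the only test named for the primary comparison has exact two-sided size 9.1% in the planned randomized patients and 12.5% at the counts used for power. In the harm direction this is more than three times the nominal 2.5% (8.4% and 11.8%). At 117 vs 39, the claim of over 80% power at alpha 0.05 for 14.8 points is not met by the level-holding tests examined, which give 62% to 68%.

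The result assumes the pooled-dose comparison, independent binomial counts, a common rate near 5% and no continuity correction. It weakens as the event rate rises and does not bear on the stopping decisions.

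**What to change.** In 10.1.2 and 10.2, replace the unpooled chi-square with one named test that holds alpha, and say that it is the primary analysis. One option is the mid-p Fisher test with two-sided p equal to twice the smaller one-sided mid-p; its size is at most 4.9% for any common rate up to 40%. Report the risk difference with a Miettinen-Nurminen (score) 95% interval.

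Apply both to all randomized patients, as 5.4.2 requires, rather than to 6-week completers. State how patients randomized but never dosed are counted, because events "will be monitored and recorded from just after the first study drug or placebo administration" (7.4.2). Restate the detectable difference at 80% power and a 5% placebo rate: about 14.8 to 14.9 points at 150 vs 51, or about 17.5 if the analysis stays at 117 vs 39.

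The cost is two sentences and one rerun of the power calculation before unblinding, with no change to data collection. Mid-p is not strictly exact: its size reaches 5.15% at 150 vs 51 for rates near 50%. Fisher's test avoids that but needs about 16 points. Pooled chi-square is the smallest edit, with size up to about 5.2% over rates to 50% and 78% power at 14.8 points.
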